## 10. SAFETY

### 10.1 Medical Device Category C studies

All adverse events (AE) including all serious adverse events (SAE) are collected, fully investigated and documented in the source document and appropriate case report form (CRF) during the entire study period, i.e. from patient's informed consent until the last protocol-specific procedure, including a safety follow-up period. Documentation includes dates of event, treatment, resolution, assessment of seriousness and causal relationship to device and/or study procedure.

The information on AEs is systematically collected by the clinician at each study visit. They will follow the procedures outlined in SOP-Medical Device Incident Reporting. The subjects are asked to keep a diary and write down any unexpected events. During the regular clinic visits the subjects are then asked questions about the event to gather details and to determine the severity of the event. If a subject reports pain that results in the inability to use the device he will be withdrawn from the study in order to avoid any pain from using the device and to remove partial data from the study. For reports of pain caused by insertion or the dome itself, the problem can be addressed in the clinic. For example, a different style or size of dome can be placed on the hearing aid, and re-training of insertion can be performed with the subject to avoid wrong or forceful insertion of the device. For reported pain they will be advised to not wear the device for 24 hours before resuming use.

Foreseeable adverse events outlined in the risk management file include discomfort caused by the domes, domes or filters falling off in the ear, no amplification coming from the device causing alarms or traffic to not be heard by the subject, skin reaction if chemical profile of device is changed, maximum output of the device exceeding 132 dB SPL, battery exploding or catching fire, and the device affecting other medical devices worn by the subject,. The incidence of all of these risks or adverse events is improbable. To mitigate the risk, the IFU describes how to insert the device, how to change the domes, and how to change a battery in case of no amplification. The IFU describes how to clean the device, domes, and filters in order to not introduce cleaning agents that might change the chemical profile of the hardware of the device. The labelling warns of the potential maximum output of the device. The IFU instructs the user to keep the device away from explosive environments, The IFU warns of interference with implantable devices.

#### 10.1.1 Definition and Assessment of (Serious) Adverse Events and other safety related events

##### Adverse Event (AE)

Any untoward medical occurrence, unintended disease or injury or any untoward clinical signs (including an abnormal laboratory finding) in participants, users or other persons whether or not related to the investigational medical device [ISO 14155: 3.2].

This includes events related to the IMD or the RMD and to the procedures involved. For users or other persons this is restricted to events related to the IMD.

##### Adverse Device Effect (ADE)

Adverse event related to the use of an investigational medical device [ISO 14155: 3.1].

This includes any adverse event resulting from insufficient or inadequate instructions for use, deployment, implantation, installation, operation, or any malfunction of the investigational medical device. This includes any event that is a result of a use error or intentional misuse.

AEs/ADEs include:

- Exacerbation of a pre-existing disease or condition.
- Increase in the frequency or intensity of a pre-existing episodic disease or medical condition.
- Any disease or medical condition detected or diagnosed after treatment with the study intervention device even though it may have been present yet undetected prior to the start of the clinical investigation.
- Any continuous persistent disease or symptoms present at baseline that worsen following the start of the clinical investigation.

Page 35 of 50

CONFIDENTIAL

---

BF001-1611, Clinical Protocol, Version 3.0, Final, Version date 02.01.2017, Page 35 of 50

- Events considered by the investigator to be related to any of the clinical investigation-mandated procedures.
- Abnormal assessments, e.g. physical examination findings, will be reported as AEs/ADEs if they represent a clinically significant finding that was not present at baseline or that has significantly worsened during the course of the clinical investigation.
- Test abnormalities will be reported as AEs/ADEs if they represent a clinically significant finding, symptomatic or not, which was not present at baseline or has significantly worsened during the course of the clinical investigation.

AEs/ADEs do not include:

- Pre-planned interventions or occurrences of endpoints specified in the CIP are not considered AEs/ADEs, if not defined otherwise.
- Unrelated medical or surgical procedures, e.g. surgery, endoscopy, tooth extraction, transfusion. However, the event leading to the procedure may be considered an AE. If this event is serious, the procedure will be described in the SAE/SADE narrative.
- Any pre-existing disease or medical condition that remains stable and does not worsen during the course of study participation.
- Situations in which an adverse change did not occur, e.g., hospitalizations for unrelated cosmetic elective surgery or for social and/or convenience reasons.

## **Serious Adverse Event (SAE)**

Adverse event that:

- results in death, or
- led to a serious deterioration in health that either:
  - results in a life-threatening illness or injury, or
  - results in a permanent impairment of a body structure or a body function, or
  - required in-patient or prolonged hospitalization, or
  - results in medical or surgical intervention to prevent life threatening illness or injury or permanent impairment to a body structure or a body function
- led to fetal distress, death or a congenital abnormality or birth defect. [ISO 14155: 3.37].

This includes device deficiencies that might have led to a serious adverse event if a) suitable action had not been taken or b) intervention had not been made or c) if circumstances had been less fortunate. These are handled under the SAE reporting system. A planned hospitalization for pre-existing condition, or a procedure required by the protocol, without a serious deterioration in health, is not considered to be a serious adverse event.

## Device deficiency

Inadequacy of a medical device related to its identity, quality, durability, reliability, safety or performance, such as malfunction, misuse or use error and inadequate labelling [ISO 14155: 3.15].

## Health hazards that require measures

Findings in the trial that may affect the safety of study participants and, which require preventive or corrective measures intended to protect the health and safety of study participants.

## **Severity of adverse events/adverse device effects**

The severity of clinical AEs is graded on a three-point scale: mild, moderate and severe, and reported in the CRF. If the severity of an AE worsens during medical device administration, only the worst intensity should be reported on the CRF. If the AE lessens in intensity, no change in the severity is required.

**Mild:** Event may be noticeable to subject; does not influence daily activities; the AE resolves spontaneously or may require minimal therapeutic intervention;

**Moderate:** Event may make subject uncomfortable; performance of daily activities may be influenced; intervention may be needed; the AE produces no sequelae.

**Severe:** Event may cause noticeable discomfort; usually interferes with daily activities; subject may not be able to continue in the study; the AE produces sequelae, which require prolonged therapeutic intervention.

### Causal Relationship of Adverse Events

A causal relationship towards the medical device or study procedure should be rated as follows:

- **Not related:** The event is definitely not associated with device application or with study procedures; a relationship can be ruled out.
- **Possibly related:** The relationship between device application or study procedures and the event is possible, but other causes cannot definitely be ruled out.
- **Related:** The event is definitely associated with device application or study procedures.

Device deficiencies that might have led to an SAE are always related to the medical device.

### 10.1.2 Reporting of (Serious) Adverse Events and other safety related events

#### Reporting to Sponsor:

The following events are to be reported to the Sponsor within 24 hours upon becoming aware of the event:

- All SAEs
- Health hazards that require measures
- Device deficiencies

The Sponsor will evaluate SAEs with regard to causality and seriousness. Device deficiencies are assessed regarding their potential to lead to an SAE.

#### Reporting to Authorities:

In Category C studies it is the local Investigator's responsibility to report **serious adverse events** in Switzerland which are

- related or possibly related to the medical device under investigation
- related or possibly related to study procedures

within 7 days to the local Ethics Committee. The Sponsor-Investigator reports within the same timeline to Swissmedic (incl. events from abroad).

- **Health hazards** that require measures are reported within 2 days

#### Periodic safety reporting

In Category C studies a yearly safety update-report is submitted by the Investigator to the Ethics Committee and by the Sponsor-Investigator to Swissmedic.

## 11. STATISTICAL METHODS

[figure not shown]
The goal of the trial is to show that the IMD performs at least as well as the marketed RMD. The platform that supports the IMD shows promising capabilities in terms of processing power and wireless capabilities. The intention with the development of the new generation is to port the main functionalities (amplification, feedback canceller, directional microphones and noise reduction) from the RMD to the IMD. For this reason, it is not expected to find that the IMD outperforms the marketed RMD.

### 11.1 Hypothesis

The goal of the test is to show that the IMD performs at least as well as the marketed RMD. A superiority hypothesis is used when a difference between performances is expected. To show that two devices have the same effect, the Committee for Proprietary Medicinal Products (CPMP) (2005) recommends using a non-inferiority test.

The non-inferiority margin is computed from the findings of the testing performed on the current marketed RMD with the primary outcomes (SRT) and other published results summarized in a meta-analysis. Lower SRT indicates a better performance, i.e. a positive difference between unaided and aided indicates an improvement with amplification.

Test condition labels: the marketed RMD as the Control (C), the IMD as the Test (T), and the non-inferiority Margin ( $\delta$ ). Positive value of  $SRT_C - SRT_T$  indicates an improvement with T:

Under  $H_0$ : the IMD is not non-inferior to the RMD:

[figure not shown]
$$C - T \leq -\delta$$

Under  $H_1$ : the IMD is not inferior to the RMD:

$$C - T > -\delta$$

Non inferiority margin is set with the following rationale (S. Kaul et al., 2005): “One proposal for selecting the margin is to take one-half of the magnitude of the worst limit of this CI—the so-called “50% rule” or “95-95 method” recommended by the FDA” with unaided condition instead of placebo.

The reference effect (unaided-aided) is about 2 dB improvement ( $SD = 2$  dB). The lowest bound of the confidence interval is 1.3 dB. Following this rationale ( $\delta = E_{\text{95-95}} - 0.5 \times C_{\text{95-95}}$ ), we will set the non-inferiority margin to 1.3 dB. This rationale can be illustrated as follows (based on D’Agostino et al., 2003):

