3.1 Non-Inferiority margin determination

Non inferiority margin set with the following rationale (S. Kaul et al., 2005): "One proposal for selecting the margin is to take one-half of the magnitude of the worst limit of this Cl—the so-called "50% rule" or "95-95"

[figure not shown]

method" recommended by the FDA" with unaided condition instead of placebo.

Some considerations:

Assay sensitivity: "the ability to detect differences between treatments if such differences exist." Metaanalysis on effect size (see section 1.2) has shown that there is a positive effect of amplification with speech reception threshold measure (effect = 0.82, SE = 0.41, and p = 0.04).

Constancy assumption: "which assumes that the historical difference between the active control and placebo will be constant in the setting of the current active control trial if a placebo control had been used." Experimental factors like speech material, noise location, and hearing aid type has no significant influence on the amplification effect size. However, we think that the reference test (16REF) presents most similarities with the experimental test design. As the differences are very small regarding the overall effect, we will use the confidence interval of 16REF, for the computation of the non-inferiority margin.

n.i.m.<-2-reviewSummary\$ci.low[reviewSummary\$study=="16REF"]/2
round(n.i.m., 1)

[1] 1.3

The non-inferiority margin for the trial will be set to 1.3 dB.

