3.3 Switching to superiority hypothesis

If the confidence interval for the difference between both devices lies entirely above 0, then "it is acceptable to calculate the P value associated with a test of superiority and to evaluate whether this is sufficiently small to reject convincingly the hypothesis of no difference. There is no multiplicity argument that affects this interpretation because, in statistical terms, it corresponds to a simple closed test procedure. Usually this demonstration of a benefit is sufficient on its own, provided the safety profiles of the new agent and the comparator are similar."

Reference: Committee for Proprietary Medicinal Products (CPMP). (2001). Points to consider on switching between superiority and non-inferiority. British Journal of Clinical Pharmacology, 52(3), 223–228.

4. Required sample size

Reference: Chow S, Shao J, Wang H. 2008. Sample Size Calculations in Clinical Research. 2nd Ed. Chapman & Hall/CRC Biostatistics Series. page 52.

With the following requirements: non-inferiority margin: 1.34, standard deviation: 2 dB, alpha: 0.025, beta: 0.1.

Required sample size:

```
delta <- n.i.m.

sd <- reviewSummary$standev[reviewSummary$study=="16REF"]

alpha <- 0.025

beta <- 0.1
```

out.sample.size <- (sd*(qnorm(1-alpha)+qnorm(1-beta))/delta)^2 ceiling(out.sample.size)

[1] 24

A sample size of 24 will be use to test the non-inferiority hypothesis with a non-inferiority margin of 1.3 dB.

5.References

Alworth, L. N., Plyler, P. N., Reber, M. B., & Johnstone, P. M. (2010). The effects of receiver placement on probe microphone, performance, and subjective measures with open canal hearing instruments. Journal of the American Academy of Audiology, 21(2010), 249–266. http://doi.org/10.3766/jaaa.21.4.4

Committee for Proprietary Medicinal Products (CPMP) (2001). Points to consider on switching between superiority and non-inferiority. British Journal of Clinical Pharmacology, 52(3), 223–228.

D'Agostino, R. B., Massaro, J. M., & Sullivan, L. M. (2003). Non-inferiority trials: design concepts and issues - the encounters of academic consultants in statistics. Statistics in Medicine, 22(2), 169–86. http://doi.org/10.1002/sim.1425

Del Re, A. C. (2015). A Practical Tutorial on Conducting Meta-Analysis in R. The Quantitative Methods for Psychology, 11 (1), 37-50.

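### The 1.3 dB non-inferiority margin is about twice what the 50% rule cited for it gives (0.655 dB)

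*Protocol*

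**What the plan says.** Protocol 11.1 cites the 50% rule, or 95-95 method, with the unaided condition standing in for placebo. The rule is to "take one-half of the magnitude of the worst limit of this CI". The section gives a reference effect of about 2 dB (SD 2 dB) and adds: "The lowest bound of the confidence interval is 1.3 dB". It then prints a formula, E - 0.5 x C with both terms subscripted 95-95, and concludes "we will set the non-inferiority margin to 1.3 dB". An illustration is announced ("This rationale can be illustrated as follows") but is not visible in the text available for this review.

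SAP 3.1 cites the same rule and names the source of the interval: "we will use the confidence interval of 16REF, for the computation of the non-inferiority margin". The table in SAP 2.1 gives 16REF a mean of 2.0 dB, SD 2.0, n = 35 and a lower limit of 1.31 dB. The code line, which begins "n.i.m.<-2-reviewSummary", takes 2 minus half of that lower limit. The section ends: "The non-inferiority margin for the trial will be set to 1.3 dB". SAP 4 carries the less rounded figure into the sample size: "With the following requirements: non-inferiority margin: 1.34, standard deviation: 2 dB".

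**The concern.** The margin is the decision threshold of the primary test, and the only rationale visible for it is a rule that gives a different number. The mismatch is easy to miss because the rounded margin (1.3) equals the rounded lower limit (1.3).

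At stake is what a positive result may claim. A reader told that the margin follows the 50% rule will take non-inferiority to mean that the investigational device (IMD) keeps at least half of the conservatively estimated benefit of the marketed device (RMD). A 1.3 dB margin does not support that. The synopsis calls the analysis exploratory, but 11.1 states a formal hypothesis against this margin, 11.2 powers the study on it, and 4.1 describes the study as final validation before release for sale.

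**Working it through.** **Inputs.** 16REF: mean 2.0, SD 2.0, n = 35, lower limit 1.31 (SAP 2.1). One-sided alpha 0.025 and 90% power (protocol 11.2, SAP 4). About 35 participants (synopsis), with complete-case analysis (protocol 11.5).

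**1. The plan's own figures reproduce.**
- Interval: 2 ± t(0.975; 34) x 2/√35 = 1.313 to 2.687.
- Coded margin: 2 - 1.313/2 = 1.344, printed as 1.34 in SAP 4 and 1.3 in SAP 3.1.
- Sample size: n = [SD x (z(0.975) + z(0.90)) / margin]² = 23.4 at 1.34, so 24. At 1.3 it is 24.9, so 25.

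**2. The cited rule.** 0.5 x 1.31 = 0.655 dB. The ratio 1.3/0.655 is 1.98.

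**3. The printed formula.** If E and C are both the 1.3 dB lower limit, E - 0.5 x C = 1.3 - 0.65 = 0.65, which agrees with the rule. It reaches 1.3 only if E is the 2 dB point estimate, and then it is not the rule.

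**4. Direction.** Hold the mean at 2 dB and vary the lower limit.

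| Lower limit (dB) | Coded margin | Cited rule |
|---|---|---|
| 1.31 | 1.345 | 0.655 |
| 0.5 | 1.75 | 0.25 |
| 0 | 2.0 | 0 |

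With the code, weaker evidence of benefit permits a larger loss. The rule does the opposite.

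**5. Retention, with the assumed RMD benefit stated.**
- RMD benefit 2 dB, margin 1.3: (2 - 1.3)/2 = 35%.
- RMD benefit 1.31 dB, margin 1.3: (1.31 - 1.3)/1.31 = 0.8%.
- RMD benefit 1.31 dB, margin 1.34: (1.31 - 1.34)/1.31 = -2.3%.
- RMD benefit 1.31 dB, margin 0.655: 50%.

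**6. Power** (paired t, non-central t, one-sided 0.025, true difference 0).

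| Complete cases | 1.3 dB, SD 2 | 0.655 dB, SD 2 | 0.655 dB, SD 1.5 | 0.655 dB, SD 1 |
|---|---|---|---|---|
| 35 | 96% | 47% | 71% | 96% |
| 30 | 93% | 41% | 64% | 93% |
| 24 | 86% | 34% | 54% | 87% |

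For 90% power at 0.655 dB (plan's z formula to exact t): 98-100 cases at SD 2, 56-58 at SD 1.5 and 25-27 at SD 1. SD 2 is the unaided-aided SD of 16REF. The documents give no SD for the RMD-IMD difference, so this range is an assumption.

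**7. Error rates.** If the true loss is 1.3 dB, the 1.3 dB test passes 2.5% of the time, as intended. If the true loss is 0.655 dB, it passes with 35 cases about 46% of the time at SD 2, 70% at SD 1.5 and 96% at SD 1.

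**The case against.** The best defence is that the formula has its own logic. If the RMD benefit really is 2 dB, an IMD that is worse by the coded 1.344 dB still keeps 0.656 dB, which is half of the lower limit. At the rounded 1.3 dB it keeps 0.7 dB, or 0.7/1.31 = 53% of that limit. This may be how a 50% entered the formula, although the text does not say so. It treats the 2 dB estimate as certain, so it is less conservative than the rule and is not the rule cited. What stands is that any retention percentage must name the RMD benefit it assumes.

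Other points in the plan's favour also stand:
- The announced illustration may define E and C, so it is safe to say only that the visible text lacks a justification. No definition makes 1.3 equal half of 1.31, and the SAP code shows what was computed.
- Type I error is 2.5% against the stated 1.3 dB.
- SAP 1 only recommends retaining some of the control's advantage over unaided, without naming a share.
- Unaided, RMD and IMD are all measured at Visit 6, so benefit over unaided can be observed directly. However, protocol 5.1 and 11.4.2 use the unaided condition only if non-inferiority is not shown.
- The 1.34 dB in SAP 4 is a sample-size input, not the decision threshold.
- The power loss at 0.655 dB depends heavily on the assumed SD.

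None of these removes the mismatch between the cited rule and the margin.

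**Conclusion.** The concern holds and must be fixed. The rule cited in protocol 11.1 and SAP 3.1, applied to the interval that SAP 3.1 names, gives 0.655 dB; the plan uses 1.3 dB, about twice as much. This conclusion needs no outside figure. The calculation itself was carried out consistently; the fault is that the formula applied is not the rule cited for it.

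The primary test remains valid as a test against a 1.3 dB loss. What fails is any reading of its result as 50% retention. The power and sample-size figures rest on equal devices and on the assumed RMD-IMD SD of 1 to 2 dB.

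**What to change.** Choose one option before any data are seen.

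**A. Follow the rule.** Set the margin to 0.5 x 1.31 = 0.655 dB (0.65 if rounded down) in protocol 11.1, 11.2 and the synopsis, and in SAP 3.1 and SAP 4. Change the code line to half the lower limit. Remove the E - 0.5 x C formula, or define its terms so that it agrees. Strike the statements of 90% power with 24 subjects in the synopsis and 11.2, and the sample size of 24 in SAP 4. Keep about 35 participants and insert:

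> Power at one-sided 0.025, assuming equal devices, for an RMD-IMD SD of 2 / 1.5 / 1 dB is 47% / 71% / 96% with 35 complete cases, 41% / 64% / 93% with 30 and 34% / 54% / 87% with 24. SD 2 dB is the unaided-aided SD of 16REF; no RMD-IMD SD was available. About 98-100 complete cases would be needed for 90% power at SD 2 dB.

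Cost: wording in five places and one line of code, with no added visits or tests. The real cost is power. With 35 complete cases it falls from 96% to 47% at SD 2, but it is still 96% at 0.655 dB if the SD is 1.

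**B. Keep 1.3 dB.** Delete the attribution to the 50% rule in 11.1 and SAP 3.1, and justify a 1.3 dB loss on its own terms. State that this margin keeps 35% of the benefit if the RMD benefit is 2 dB and about 1% if it is 1.31 dB, so a non-inferiority conclusion does not claim 50% retention. Optionally, add a supportive retention contrast from the Visit 6 unaided, RMD and IMD data, outside the primary decision rule.

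Cost: a written justification and two deletions. Sample size, visits and the primary test are unchanged, but the 50% rule can no longer be cited in support.

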## 11.2 Determination of Sample Size

For non-inferiority testing, sample size calculations are the same as those for a 1-tailed test for superiority when the specified  $\delta$  is the same as the superiority population difference to detect (Masha & Sessler, 2011). The sample size calculation follows the recommendation from Chow & Wang (2008), where  $sd$  is the standard deviation,  $\alpha$  the significance level,  $1-\beta$  the power, and  $\delta$  the non-inferiority margin:

$$n = \frac{sd^2 \times (z_{1-\alpha} + z_{1-\beta})^2}{\delta^2}$$

For 90% power at the 0.025 significance level, the required sample size is about 24 subjects to detect non-inferiority of the marketed RMD with an SD of 2 dB and non-inferiority  $\delta$  of 1.3 dB. (Chow & Wang, 2008, p. 52).

